13.14 End of Study Definition

The end of the double-blind, placebo-controlled period of the study is defined as the completion of the last follow-up visit of the last enrolled subject who elects not to participate in the OLE period of the study.

For subjects electing to enter the OLE period of the study, the end of the OLE period of the study is defined as the completion of the last follow-up visit for the last subject.

The enrollment of the last subject in the double-blind period of the study is anticipated to occur in 2023. The last subject's last follow up visit will be approximately 24 weeks after the date of enrollment if OLE is not elected, or up to 36 weeks after the date of enrollment if the OLE is elected.

Please refer to Section 14.12 for the study ending prematurely.

14. Adverse Event Reporting and Documentation

14.1 Adverse Events

In accordance with 21 Code of Federal Regulation (CFR) 312.32(b) and International Conference on Harmonization (ICH) Guidance E2A, an AE is any untoward medical occurrence in a clinical investigation of a subject administered a pharmaceutical product and that does not necessarily have a causal relationship with the treatment.

An AE is therefore any unfavorable and unintended sign (including an abnormal laboratory finding), symptom, or disease temporally associated with the administration of an investigational product, whether or not related to that investigational product. An unexpected AE is one of a type not identified in nature, severity, or frequency in the current Investigator's Brochure or of greater severity or frequency than expected based on the information in the Investigator's Brochure.

Examples of an AE include:

- Significant worsening or exacerbation of underlying medical condition.
- Significant abnormal findings from physical exams, vital signs, or laboratory tests.

The following examples are not considered AE:

- Medical or surgical procedure, although the condition leading to the procedure is usually an AE.
- Anticipated day-to-day fluctuations of preexisting medical conditions (including laboratory values) as long as significant worsening from baseline does not occur.
- Signs or symptoms of the disorder being studied unless they become more severe or occur with greater frequency than occurring at baseline.

All AE, whether elicited by questions from study staff, volunteered, or noted on physical examination/laboratory testing, and regardless of causality or severity, will be assessed and recorded in the eCRF beginning after the first administration of study drug in the double-blind period of the study and ending at the time of study completion or ET of the double-blind period or the OLE period, whichever is later.

For subjects participating in the OLE period, AE will be recorded in the CRF of the AK002-027 double-blind treatment period database up until the first administration of lirentelimab in the OLE period and recorded in the CRF of the AK002-027 OLE period database beginning from the time of first administration of lirentelimab ending at the time of study completion or ET of the OLE period.

14.2 Serious Adverse Events

A SAE is defined as an AE that meets that one of the following criteria:

- Death
- A life-threatening AE that places the subject at risk of death at the time of the event. It does not refer to an event that hypothetically might cause death if it were more severe.
- Inpatient hospitalization or prolongation of existing hospitalization.
- A persistent or significant disability/incapacity.
- A congenital anomaly/birth defect occurring in the offspring of a study subject.

• Other important medical events may also be considered a SAE when, based on appropriate medical judgment, they jeopardize the subject or require intervention to prevent any of the outcomes listed above.

Serious adverse events will be assessed and recorded beginning after the first administration of study drug and ending at Day 155 (\pm 5) or 84 (\pm 5) days after last dose, unless the SAE is related to a screening procedure, in which case it will be captured from the date of informed consent.

14.3 Adverse Events of Special Interest

Adverse Events of Special Interest (AESI) for this study include:

- Malignancies confirmed by histopathological report. (Mast cells and eosinophils are part of the normal immune response. By decreasing their function, lirentelimab could theoretically increase the risk of malignancy.)
- Parasitic infections confirmed by positive clinical laboratory test. (Eosinophils are believed to be involved in protecting the body from parasitic infections. Decreasing their function could theoretically increase the risk of parasitic and opportunistic infections.)
- Opportunistic infections (infections known to be more severe or occur more frequently in immunosuppressed populations) as confirmed by positive clinical laboratory test.
- Injection-related reactions and hypersensitivity reactions, including anaphylaxis.

Adverse Events of Special Interest will be assessed beginning after the time of first administration of study drug and ending on Day 155 (\pm 5) or 84 (\pm 5) days after last dose. Any new AESI (or new information related to a previously reported AESI) must be recorded in the AE eCRF and designated as an "AE of special interest."

14.4 Injection-Related Reactions

All AE considered by the Investigator *to be related to the biological substanc*e and occurring within 24 hours of the start of the SC injection of study drug should be captured as 1 IRR. Common symptoms of IRR may include but are not exclusive to:

- Flushing
- Chills
- Back or abdominal pain
- Chest discomfort or tightness
- Dizziness

- Nausea
- Vomiting
- Sweating
- Fever
- Urticaria

- Shortness of breath
- **Pruritus**
- Headache

- Bronchospasm
- Hypotension or hypertension

All symptoms experienced by a subject during an IRR will be listed in the eCRF under 1 IRR, unless the Investigator believes a symptom is not part of the IRR, in which case it will be recorded separately. The start time of the IRR will be captured as the start time of the first symptom, and the end time of the IRR will be captured as the end time of the last symptom.

14.5 **Injection Site Reactions**

All AE considered by the Investigator to be related to the SC administration of the biological substance at the injection site and occurring within 24 hours of the start of the injection should be captured as 1 injection site reaction (ISR).

Common symptoms of ISR include, but are not exclusive to:

- Redness at the injection site
- Itching at the injection site
- Swelling at the injection site (beyond the bump caused by the volume of the drug injected under the skin)
- Bruising at the injection site
- Burning at the injection site
- Pain at the injection site

All symptoms experienced by the subject during an ISR will be listed in the eCRF under 1 ISR, unless the Investigator believes a symptom is not part of the ISR, in which case it will be recorded separately. The start time of the ISR will be captured as the start time of the first symptom, and the end time of the ISR will be captured as the end time of the last symptom.

14.6 **Anaphylaxis**

A suspicion of anaphylaxis will be carefully monitored and treated according to standard of care. Emergency crash cart equipment and medications, including multiple doses of epinephrine, vasopressors, and bronchodilators, will be available at all times during the conduct of the study. To define anaphylactic reactions in a consistent and objective manner, all AE of suspected anaphylaxis will be evaluated using Sampson's Criteria for Anaphylaxis (Appendix 7). The assessment of an AE will be done pursuant to definitions set forth by ICH Good Clinical Practice (GCP) guidelines and applicable regulatory requirements.

If a subject experiences signs or symptoms of anaphylaxis, they should be treated with standard of care, such as epinephrine, diphenhydramine, acetaminophen, methylprednisolone, and other supportive measures along with cessation of the SC injection. A sample of blood should be obtained for plasma histamine level and tryptase within 1–2 hours of the onset of symptoms. Also, an unscheduled ADA blood sample may be obtained if an immunogenicity-related AE is suspected.

14.7 Evaluating Adverse Events and Serious Adverse Events

14.7.1 Establishing Diagnosis

Whenever possible, diagnoses should be given when signs and symptoms are due to a common etiology (e.g., dysuria, urinary nitrites should be reported as a urinary tract infection). If the diagnosis is not known, individual signs and symptoms should be assessed and recorded in the AE eCRF as separate AE.

The Investigator (or qualified Subinvestigator) must assign the AE attributes listed in Table 5 (AE severity), Table 6 (relationship to study drug), and Table 7 (relationship to study procedure) and is responsible for ensuring this information is recorded in the source documentation.

14.7.2 Assessment of Intensity

Investigators will use their clinical judgment as well as the guidelines laid out in the NCI CTCAE (version 5.0 or most current version) tables to assess the intensity of each AE and SAE (Table 5 and Appendix 6).

Table 5 Adverse Event Severity per CTCAE

Grade	CTCAE Description*
1	Mild; asymptomatic or mild symptoms; clinical or diagnostic observations only; intervention not indicated.
2	Moderate; minimal, local, or noninvasive intervention indicated; limiting age-appropriate instrumental activities of daily living (ADL).
3	Severe or medically significant but not immediately life-threatening, hospitalization or prolongation of hospitalization indicated; disabling; limiting self-care ADL.
4	Life-threatening consequences, urgent intervention indicated.
5	Death related to AE.

^{*} CTCAE v. 5.0: Grade refers to the severity of the AE. The CTCAE displays Grades 1–5 with unique clinical descriptions of severity for each AE based on this general guideline.

The term "severe" is a measure of intensity, and a severe AE is not necessarily a SAE. When the intensity of an AE changes more than once a day, the maximum severity for the event should be

entered into the AE eCRF. If the intensity changes over a number of days, these changes should be recorded separately (i.e., as having distinct onset dates).

14.7.3 Assessment of Causality to Study Drug

The Investigator should use their clinical judgment as well as the guidelines in Table 6 to assess the relationship between study drug and AE.

Table 6 Adverse Event Relationship to Study Drug

Relationship to Study Drug	Comment
Related	There is clear evidence that the event is related to the use of study drug (e.g., confirmation by positive rechallenge test, if possible). Another etiology is considerably less likely.
Possible	The event cannot be explained by the subject's medical condition, concomitant therapy, or other causes, and there is a plausible temporal relationship between the event and study drug administration.
Unlikely/Remote	An event for which an alternative explanation is more likely (e.g., concomitant medications or ongoing medical conditions) or the temporal relationship to study drug administration and/or exposure suggests that a causal relationship is unlikely. (For reporting purposes, Unlikely/Remote will be grouped together with Not Related.)
Not Related	The event can be readily explained by the subject's underlying medical condition, concomitant therapy, or other causes, and therefore, the Investigator believes no relationship exists between the event and study drug.

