6.11 Safety Analyses

6.11.1 Adverse Events

Safety assessments will be based mainly on the nature, frequency, relationship, and severity of adverse events (AE). The AE will be coded by primary System Organ Class (SOC) and Preferred Term (PT) according to MedDRA (version 21.0). The treatment-emergent adverse events (TEAE) will be summarized by the number and percentage (n and %) of subjects in each SOC and PT.

For summaries by relationship to study drug, "possibly related" will be combined with "related", and "unlikely/remotely related" will be combined with "not related." When multiple AE are reported with the same PT, the AE of the strongest relation to study drug will be included in the summary by relationship, and the AE of the most severe grade will be included in the summary by severity table.

The following AE incidence tables will be presented.

- Overview of TEAE to include
 - Number (%) of subjects who reported at least 1 TEAE
 - Number (%) of subjects who reported at least 1 treatment related TEAE
 - Number (%) of subjects who reported at least 1 severe TEAE
 - Number (%) of subjects who reported at least 1 serious TEAE
 - Number (%) of subjects who reported at least 1 TEAE leading to treatment discontinuation
 - Number (%) of subjects who reported at least 1 TEAE leading to study discontinuation
 - Number (%) of subjects who reported at least 1 TEAE of special interest (TEAESI)
- TEAE by PT sorted by decreasing order of subject incidence in the combined treatment group
- TEAE by SOC and PT in alphabetical order
- TEAE by SOC, PT, and maximum severity
- TEAE by SOC, PT, and strongest relationship to study drug
- TEAE leading to treatment discontinuation by SOC and PT, if warranted by sample size
- TEAE leading to study discontinuation by SOC and PT, if warranted by sample size
- Serious TEAE by SOC and PT, if warranted by sample size
- TEAESI by SOC and PT

All AE will be listed with onset/stop day, relationship to study drug, severity, action taken, and outcome. Pertinent subject information including treatment group and demographics will also be included.

Separate listings will be provided for TEAE leading to study discontinuation, TEAE of special interest, and treatment-emergent serious AE (TESAE).

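### Table 6 bars 'Possible' for any event that CSU could also explain, so new or worsened hives or itch after an injection has no fitting causality category and may be reported as not related

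*Protocol*

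**What the plan says.** Protocol Section 14.7.3 asks investigators to combine their own judgment with the four categories of Table 6:

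- *Related*: "There is clear evidence that the event is related to the use of study drug", with any other etiology considerably less likely.
- *Possible*: "The event cannot be explained by the subject's medical condition, concomitant therapy, or other causes", and the timing is plausible.
- *Unlikely/Remote*: "An event for which an alternative explanation is more likely (e.g., concomitant medications or ongoing medical conditions"), or the timing speaks against the drug.
- *Not Related*: "The event can be readily explained by the subject's underlying medical condition, concomitant therapy, or other causes", and the investigator therefore believes that there is no relationship.

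Table 6 adds: "For reporting purposes, Unlikely/Remote will be grouped together with Not Related". Table 7 (Section 14.7.4) applies the same *Possible* wording to study procedures. SAP 6.11.1 makes the matching split "For summaries by relationship to study drug": possible joins related, and unlikely joins not related.

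Three other sections matter. Section 14.4 defines an IRR as an AE that the investigator considers related to the biological substance, "occurring within 24 hours of the start of the SC injection of study drug should be captured as 1 IRR"; urticaria and pruritus are 2 of the 15 symptoms it lists. Section 14.3 names as AESIs "Injection-related reactions and hypersensitivity reactions, including anaphylaxis". Section 14.1 says that symptoms of the disease under study are not AEs unless they are more severe or more frequent than at baseline.

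**The concern.** A usual middle category for causality covers an event that the drug may have caused although something else may have caused it too. Here the middle category asks for the opposite: no other cause may be able to explain the event. In most diseases that is a minor flaw of wording. In CSU, two of the listed reaction symptoms are the disease itself, so the competing explanation is always at hand.

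At stake is the safety classification, not the primary endpoint. Related TEAEs and AESIs are planned summaries, and IRRs are named among the safety endpoints in Protocol Section 7.1. Experience with subcutaneous dosing is limited: the only subcutaneous safety results described are from a Phase 1 study in healthy volunteers, who had no urticaria that could be confused with a reaction.

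**Working it through.** The plan states no figure on this point, so the check is mainly textual.

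**Step 1. Test one event against each category.** Take hives or itch, worse than baseline, starting a few hours after an injection, with drug and CSU equally credible as causes.

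| Category | Condition | Met? |
|---|---|---|
| Related | Clear evidence; other cause considerably less likely | No |
| Possible | No other cause can explain it; timing plausible | No, because CSU can explain it |
| Unlikely/Remote | Another cause more likely, or timing against the drug | No, because the causes are equal and the timing fits |
| Not Related | Readily explained otherwise, and no relationship believed | First part arguably yes, second part no |

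No row fits. Section 14.7.1 nevertheless requires the investigator to assign a Table 6 attribute, so one must be chosen. The two upper rows are closed by their wording. The two lower rows fail only on the investigator's degree of belief. A downward drift is therefore likely, but the text does not compel it.

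**Step 2. How often is the competing explanation available?** Inclusion criterion 4 requires UAS7 ≥16 and HSS7 ≥8 in the 7 days before Day 1.

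- UAS7: 16 / 7 = 2.3 per day on average, out of a daily maximum of 6.
- HSS7: the daily maximum is 3, and 8 / 3 = 2.67, so hives were present on at least 3 of the 7 days when all diaries are complete.

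Essentially every subject has recent hives that could explain later ones. Section 14.1 narrows the problem: symptoms no worse than baseline are not AEs and never reach Table 6.

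**Step 3. Follow a downgraded event through the outputs.**

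- Treatment-related TEAE count (SAP 6.11.1): lost.
- IRR under Section 14.4: not captured, since relatedness is part of the definition.
- AESI count by the IRR route: lost.
- AESI count by the hypersensitivity route: still open, because Section 14.3 states no relatedness condition for it. Hives put down to CSU would not, however, be recognised as hypersensitivity.
- TEAE tables by SOC and PT, and the AE listing: kept.

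**Step 4. Can the number be derived?** Phase 1 had six subcutaneous cohorts with 6 active subjects each, 6 × 6 = 36, and reported no local or systemic injection reactions. The exact two-sided 95% upper limit for 0 of 36 is 1 − 0.025^(1/36) = 0.097. If those healthy volunteers, across all dose levels, are taken as comparable with the 65 active subjects here (an assumption), that allows 0 to 65 × 0.097 = 6.3 subjects with an IRR. To go further, one needs the share of IRRs that are mainly hives or itch and the share of those that are downgraded. The documents give neither, so the calculation stops there.

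**The case against.** The case against has real weight.

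- **Judgment stays open.** Table 6 is guidance used with clinical judgment, and Section 14.4 does not refer to Table 6. By listing urticaria and pruritus, it prompts investigators to consider them. This makes the effect a tendency; it does not repair the stated rule.
- **The arm comparison survives.** The trial is blinded and placebo-controlled, all TEAEs are tabulated by arm whatever their relationship, and hives and itch are scored daily in the diary. A reader might infer that the safety signal disappears. It does not; what can be lost is its label as related or as an AESI.
- **No category fits.** A reader might infer that such events must become *Not Related*. That category also needs the investigator to believe that no relationship exists, so the text supports only *may be reported as not related*.
- **No IRR table is planned.** A reader might speak of a lost IRR count, but the SAP has no separate IRR output. IRRs enter through the AESI tables.
- **Other protections.** Suspected anaphylaxis is judged by Sampson's criteria, not Table 6. All symptoms of a recognised IRR are recorded under it, so only reactions consisting mainly of hives or itch are exposed. SAP 5.4 counts a missing relationship as related, but that helps only if the field is left blank, which Section 14.7.1 does not allow.
- **Size.** A reader might assume a 10% IRR rate in 65 subjects (6.5 IRRs), with 30% to 50% presenting as hives or itch, and infer that 2.0 to 3.3 are lost. The documents do not support this. Phase 1 subcutaneous dosing gave no reactions, the 43% IRR rate is from intravenous dosing, the common intravenous IRR symptoms in Protocol Section 2.3 do not include hives or itch, and the sum treats every such event as misclassified.

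**Conclusion.** The gap in the wording is real and worth closing. As written, Tables 6 and 7 provide no category for an AE with plausible timing that both study drug (or procedure) and CSU could explain. The practical case is new or worsened urticaria or pruritus soon after an injection. Such events could leave the treatment-related TEAE count and the IRR-type AESI count, while staying in the all-TEAE tables and listings.

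The conclusion assumes that investigators apply the Table 6 wording largely as it stands. The number of events affected cannot be derived from the documents and may be small, possibly zero. The primary endpoint is untouched.

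**What to change.** 1. In Tables 6 and 7, redefine *Possible* as: plausible temporal relationship and a contribution of study drug (or procedure) cannot be ruled out, even though other causes may also explain the event.
2. In SAP 6.11.1, add a by-arm table of TEAEs, including urticaria and pruritus, with onset within 24 hours of an injection, regardless of assigned relationship. If only onset dates are available for some events, state a date-based rule such as the day of injection or the following day.

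**Cost.** The first change touches two table cells but is a protocol amendment under Section 18.1, with retraining at up to 70 sites in three countries. The related-AE rate would rise somewhat in both arms. Section 13.14 expects the last subject to be enrolled in 2023 and the SAP is dated 03 November 2023, so a change now could leave two causality definitions within one trial. The second change avoids that: it uses data already collected, needs only a SAP amendment before database lock and one extra table, and does not depend on causality labels. If only one change is practical at this stage, make the second.

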14.7.4 Assessment of Causality to Study Procedure

The Investigator should use their clinical judgment as well as the guidelines in Table 7 to assess the relationship between study procedure and AE. Assessment of causality to study procedure should include causality to such items as blood draw (as appropriate), or other.

 Table 7
 Adverse Event Relationship to Study Procedure

Relationship to Study Procedure	Comment
Related	There is clear evidence that the event is related to a study procedure.
Possible	The event cannot be explained by the subject's medical condition, concomitant therapy, or other causes, and there is a plausible temporal relationship between the event and a study procedure.
Unlikely/Remote	An event for which an alternative explanation is more likely (e.g., concomitant medications or ongoing medical conditions) or the temporal relationship to any study procedure suggests that a causal relationship is unlikely (For reporting purposes, Unlikely/Remote will be grouped together with Not Related).
Not Related	The event can be readily explained by the subject's underlying medical condition, concomitant therapy, or other causes, and therefore, the Investigator believes no relationship exists between the event and a study procedure.

